The MRI imaging with ferumoxytol as a contrast agent will be conducted at the scheduled visits based on timing of FGR diagnosis. We will administer ferumoxytol in a hospital triage setting with maternal pulse and blood pressure monitoring and fetal heart rate monitoring. The pharmacy will be notified in advance of the arrival of the patient, so that they can prepare the infusion in a timely fashion and deliver it to triage upon patient's arrival. Subjects will arrive at UnityPoint-Health Meriter Hospital obstetric triage unit as prescheduled for ferumoxytol infusion. Later that same day, the subjects will present to the UW Hospital, WIMR or [name] location for their pre-scheduled MRI. In the triage unit, the nurse will obtain baseline vital signs, including maternal pulse, blood pressure, and fetal heart rate. Following this, the nurse will initiate an infusion dose of ferumoxytol. We plan to administer Ferumoxytol intravenously, by infusion, over 30 minutes. The patients will be monitored at 5 to 15-minute intervals, for pulse, blood pressure, respiration, and fetal heart rate. The MRI scanning procedure will be conducted at the UW Hospital, WIMR or [name] location for approximately 60 minutes.

The recommended dose of Feraheme is an initial 510 mg dose followed by a second 510 mg dose 3 to 8 days later. We plan to dilute half of the recommended initial dose, i.e. 255 mg in 50 mL of 0.9% Sodium Chloride Injection, USP or 5% Dextrose Injection, USP. We will give Feraheme only once, in one infusion of 255 mg to each subject who has consented for this study.

2-3 weeks after the ferumoxytol infusion you will be asked to return to Meriter-Hospital for a blood draw to assess your iron levels.

Obtain clinical (obstetric) data from medical records review

All clinical data from prenatal visits including GA specific maternal weight, blood-pressure, urine protein and pregnancy dating, GA at delivery, birth weight, neonatal outcome including routine NB hearing test, data specifically regarding fetal growth restriction (FGR) and maternal complications like PE or hypertension requiring preterm delivery is recorded. We confirm normal outcomes as defined by absence of any clinical (neonatal BW percentile for GA) parameters of diagnosis of FGR and absence of any clinical evidence of PE or superimposed PE by current ACOG criteria.

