After subjects have been enrolled, the On-Study/Follow-up visit and the procedures performed at each visit are described in detail below.

Visit 1Ferumoxytol Infusion and 1st MRI

All procedures at this visit are for research purposes only. The infusion process, including setup of infusion and subject in the triage, subject monitoring and post-infusion monitoring will be performed as part of a paid service by qualified staff at UPH-Meriter Hospital triage. The MRI will be performed by qualified and trained clinical staff as part of a paid service at the locations listed below. The study coordinator will be present during all procedures.

Patients will receive an infusion of ferumoxytol and a same day MRI within 1-2 weeks of FGR diagnosis. This visit could occur anytime between 29 0/7 - 35 6/7 weeks gestation.

All subjects will arrive at UnityPoint Health-Meriter Hospital obstetric triage unit as prescheduled for ferumoxytol infusion. In the triage unit, the nurse will obtain baseline vital signs, including maternal pulse, blood pressure, and fetal heart rate. Following this, the nurse will initiate an infusion dose of ferumoxytol (dose). The patients will be monitored at 5 to 15-minute intervals, for pulse, blood pressure, respiration, and fetal heart rate, along with an adverse event review. In an adverse effect occurs, the attending physician, anesthesiologist and triage staff would be notified. This event will be handled similarly to any other medical emergency in triage. This infusion will last 30 minutes followed by 30 minutes of monitoring. However, the overall study visit is anticipated to last 1-2 hours this is to allow enough time for the patient to check in to triage and get settled before initiating the ferumoxytol infusion.

Following the ferumoxytol infusion, the patient will receive the first 60-minute MRI at the UW Hospital, WIMR or [name] location within 1-15 hours after completion of the ferumoxytol infusion. The purpose of this MRI is for the detection of intervillous placenta blood, placental lesions and detection of macrophages at implantation site:

Visit #2: 2nd MRI

All procedures at this visit are for research purposes only. The MRI will be performed by qualified and trained clinical staff as part of a paid service at the locations listed below. The study coordinator will be present during all procedures.

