Our IND application fully describes the iron metabolism, ferumoxytol safety and iron delivery to the fetus. (see section 9. Nonclinical Toxicology). In addition, as stated in the summary of our use of ferumoxytol as a MRI contrast agent in rhesus macaques in our IND application, there was “not significant ferumoxytol being transported across the placenta and into the fetus.” (see page 8 of the IND application, “Ferumoxytol Detection Following Infusion in Rhesus Macaque Pregnancy.”

All pregnant women are anemic, so there is no risk for iron overload. Long-lasting buildup is not possible, as all iron will be cleared by maternal macrophages within a few days. We describe the study of ferumoxytol use in pregnancy in our IND application and the determination of our colleagues that ferumoxytol is cleared from the blood 24 hours post-infusion. We will only be administering a single infusion in the proposed study. We will be only selecting subjects who are not at risk for iron overload and will be monitoring their iron status. We are also only using half the recommended dose that is used to treat anemia in pregnant women.

The estimated background risk of major birth defects and miscarriage for the indicated populations is unknown. All pregnancies have a background risk of birth defect, loss, or other adverse outcomes. In the U.S. general population, the estimated background risk of major birth defect and miscarriage in clinically recognized pregnancies is 2-4% and 15-20%, respectively. Most birth defects occur during the period of embryogenesis (organogenesis), which is completed in humans at 14 weeks gestation, based on menstrual history. We plan to use ferumoxytol during the 24-28 week window, which is well beyond the period of organogenesis; hence use of ferumoxytol at indicated time is unlikely to cause birth defects in study participants. Subjects with fetal birth defects diagnosed during the first trimester or at 20 weeks are excluded from the study.

Disease-associated maternal and/or embryo/fetal risk: Untreated IDA in pregnancy is associated with adverse maternal outcomes such as post-partum anemia. Adverse

pregnancy outcomes associated with IDA include increased risk for preterm delivery and low birth weight.

Preeclampsia and FGR Risks

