Specific Aim 1: MRI Flow

- 2D Phase Contrast MRI (Flow Imaging) = FDA approved, clinical sequence

Specific Aim 2: MR Perfusion and Oxygenation

- Oxygenation (BOLD MRI) – multi TE gradient echo sequence = FDA approved sequence

Specific Aim 3: MRI Ferumoxytol DCE perfusion data (not investigational sequences) and localization of immune cells.

DATA AND SAFETY MONITORING

Data and Safety Monitoring Plan

We use the UW ICTR Data Monitoring Committee for the purpose of oversight over this study. We have accounted for the fees for the Data Safety Monitoring. The clinical investigator, [name], the PI, [name] and the co-investigator [name], respectively, are responsible for reporting any adverse responses or events that occur. These are reported as per requirement to UW IRB, and to the Data Monitoring Committee. We take advice from the IRB committee and Data Monitoring Committee for appropriate modifications of our procedures in order to avoid such events.

For subjects receiving the ferumoxytol infusion, the PI and study team will monitor any potential impact on the subject and the fetus. The subject will be closely monitored by triage clinical staff during the infusion of ferumoxytol in the triage unit, including the collection of vital signs. With any signs of reactions, the infusion will be stopped. The study coordinator will report any events of this nature, including adverse events and unanticipated problems, to the PI and the DSMB within one business day.

In the weeks following infusion, the PI will discuss the imaging results with the subject and the clinician providing direct care to the subject. Any adverse events will be documented, entered into the subjects study file and reported to the DSMB. After delivery, pregnancy outcome and any potential impact on the fetus will be documented and reviewed with the PI and subject clinician and DSMB. Development of pre-

eaclampsia and FGR will not be considered, but will be reported, as an adverse event secondary to ferumoxytol infusion.

Data Monitoring Committee (DMC)

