Definitely Related: An AE categorized as Definite is clearly related to the intervention. If the timing of the AE is definitely consistent with the exposure to the study intervention and it is most likely that the AE was caused by the study intervention such as because a high occurrence of the AE was expected based on the study intervention materials? In this case, the PI may categorize the AE as definitely related.

Probably Related: An AE that is likely related to the use of the drug. A Probable AE is likely related to the intervention. If the timing of the AE is consistent with the exposure to the study intervention and it is more likely that the AE was caused by the study intervention than not, the PI may categorize the AE as Probable.

Possibly Related: An AE that may be related to the use of the drug. If the timing of the AE is reasonably consistent with the exposure to the study intervention, and there is another cause of the AE that could be equally likely, the PI may categorize the AE as Possible.

Unlikely Related: An Unlikely AE is one that is doubtfully related to the intervention. The coincidence of the AE with the exposure of the investigational product or intervention should be assessed. An AE that continued while the intervention was interrupted or stopped, or if the AE resolved while the intervention continued, may be categorized as Unlikely. If there is another more likely cause of the AE, the PI may determine that the AE was unlikely related to the study intervention.

Not Related/Unrelated: An Unrelated AE is one that is clearly NOT related to the intervention. An AE may be considered Unrelated if the subject did not receive the study intervention or if there is another obvious cause of the AE (for example, a car accident or other disease/condition).

Adverse Events of Special Interest

Adverse events pertaining to the subject (mother) or neonate child occurring after the signing of consent until 6 weeks post-delivery, will be collected. Conditions that are

routinely encountered by obstetricians or pediatricians, such as C-section or infant jaundice, will be recorded on the adverse event log, but will not be reported (i.e. entered into OnCore) per clinical investigator's judgement. All adverse events meeting the HS-IRB reportable event requirements will be entered into OnCore, regardless of being considered a routine condition.

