Adverse events that are expected in pregnancy and assessed as not related/unrelated to the protocol will not be reported to the ICTR DMC and entered into OnCore. These events include but are not limited to nausea and vomiting, dizziness, abdominal discomfort, back pain, vaginal discharge, and Braxton Hicks contractions.

Given the exclusion criteria and MRI screening, we do not anticipate any major events related to the MRI procedure. However, it is possible that patients report claustrophobia or anxiety in the large bore MRI machines. This may potentially require that we reduce the BMI cutoff from 39.9 Kg/m² to a lower value for the purpose of our study examination. The adverse response and claustrophobia concerns, even in a wide bore MRI research equipment, is one of the reasons we are choosing the BMI range of 18.5-39.9 Kg/m² for our study purposes.

Any planned hospitalizations for the delivery will not be reported as an SAE, but if any AE occurs during delivery or if the hospitalization is lengthened due to safety concerns this will be reported.

Genetic conditions, birth defects, or cardiac defects not recorded or suspected prior to consent will be documented as adverse events.

Any event may be documented and followed for up to 1 year post-delivery upon investigator's discretion.

Serious Adverse Event Reporting Requirements

Adverse Events that are:	Notify HS IRB	Notify DMC	Notify FDA** (events related to Ferumoxytol-MRI only)
Serious Suspected/Related* Unexpected	Within 14 business days	Within 14 business days	Notify FDA and all participating institutions as soon as possible, but no later than 15 calendar days after learning of the event
Serious Life threatening or Fatal Suspected/Related* Unexpected	Within 1 business day (24 hours) of learning of the event.	Within 1 business day (24 hours) of learning of the event.	Within 7 calendar days of learning of the event

* The UW-Madison HSIRB requires immediate reporting of serious adverse events that are probably or definitely related, whereas the FDA requires reporting of these events that are possibly, probably or definitely related. Therefore if an event is reported to the HSIRB, the event will also be reported to the FDA.

Reporting requirements to the ICTR Data Monitoring Committee

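### For a single 30-minute ferumoxytol infusion, the dechallenge test in the Unlikely definition cannot discriminate, and it permits a grade below every relatedness-based expedited reporting threshold

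*Combined protocol and SAP*

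**What the plan says.** Assessment of Attribution defines five grades, from Definitely Related to Not Related. Under Unlikely Related it asks the assessor to consider how the AE coincides with exposure, and then adds: "An AE that continued while the intervention was interrupted or stopped, or if the AE resolved while the intervention continued, may be categorized as Unlikely".

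The intervention is a single short administration. Ferumoxytol administration, Preparation, and Dosing and Administration all state: "We will give Feraheme only once, in one infusion of 255 mg to each subject who has consented for this study". Visit 1 adds: "This infusion will last 30 minutes followed by 30 minutes of monitoring". The Data and Safety Monitoring Plan says: "With any signs of reactions, the infusion will be stopped".

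Impact on the Fetus describes how long the agent stays in the body. It says that "ferumoxytol is cleared from the blood 24 hours post-infusion" and that "all iron will be cleared by maternal macrophages within a few days".

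AEs in mother or neonate "occurring after the signing of consent until 6 weeks post-delivery, will be collected" (Adverse Events of Special Interest). For serious events, the footnote to the table in Serious Adverse Event Reporting Requirements has the IRB requiring immediate reports of probably or definitely related events, "whereas the FDA requires reporting of these events that are possibly, probably or definitely related".

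**The concern.** Dechallenge reasoning belongs to continuing treatment: if the drug is withdrawn and the event carries on, the drug becomes a less likely cause. With one 30-minute infusion nothing is withdrawn in that sense. The infusion simply ends while, on the protocol's own account, the agent is still in blood and later in macrophages. Persistence past the end of infusion therefore says almost nothing about cause, yet the definition offers it as a ground for Unlikely.

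The most awkward case is an infusion reaction. The plan has the infusion stopped at any sign of one. If the reaction does not settle at once, it has literally continued while the intervention was stopped, and the clause then supports an Unlikely grade for an event with a close time relation to the drug.

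The grade has consequences. Under Adverse Event (AE), relatedness is one of the determinants of whether an event receives an expedited report. A serious unexpected event graded Unlikely would not go to the IRB or the FDA by that route. The protocol says that the available data on ferumoxytol in pregnancy are insufficient to inform a drug-associated risk.

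**Working it through.** The plan gives no figure on this point, so there is nothing to reproduce. Two checks were made.

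**1. How often is the clause met?**

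Inputs: infusion 30 minutes (Visit 1); AE collection to 6 weeks after delivery (Adverse Events of Special Interest); earliest Visit 1 at 29 0/7 weeks (visit table). The date of delivery is an assumption, so a range is shown.

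Share of the period from the start of infusion in which the infusion is already stopped = 1 − 30 / (total minutes).

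- Shortest case, delivery on the day of infusion: 6 × 7 × 24 × 60 = 60,480 minutes; 30/60,480 = 0.05%; stopped share 99.95%.
- Long case, infusion at 29 0/7 and delivery assumed at 40 0/7: 11 + 6 = 17 weeks = 171,360 minutes; 30/171,360 = 0.02%; stopped share 99.98%.
- Triage period only (30 minutes of infusion, 30 of monitoring): 30/60 = 50% is after the stop.
- Against the stated blood clearance: 0.5 h / (0.5 h + 24 h) = 2.0% of the period is infusion. If the macrophage period is counted, the share is smaller.

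These are shares of time, not of events. They show only that nearly any event with some duration meets the clause, so the clause cannot separate related from unrelated events. The other half of the sentence (resolution while the intervention continues) has little scope: the event would have to start and end within 30 minutes with the infusion still running.

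**2. Which reporting routes does an Unlikely grade miss?**

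| Route | Section | Relatedness required | Unlikely qualifies? |
|---|---|---|---|
| IRB, expedited | Serious Adverse Event Reporting Requirements | Probable or definite | No |
| FDA, expedited | Same | Possible, probable or definite | No |
| DMC, expedited | Same; Reporting requirements to the ICTR Data Monitoring Committee | As for the IRB | No |
| Unanticipated problem | Unanticipated Problem (UP) Definition | Related or probably related | No |
| DSMB, any AE | Data and Safety Monitoring Plan | None | Yes |
| PI and DSMB within one business day, infusion reactions | Same | None | Yes |
| OnCore access for the DMC, with automatic SAE notice | Reporting requirements to the ICTR Data Monitoring Committee | None stated | Yes |
| Stopping rule, two anaphylactic reactions | Study Stopping Guidelines | None | Yes |

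The attribution-based exclusion from OnCore covers only events that are both expected in pregnancy and graded not related, so Unlikely events are not removed by it. An Unlikely grade thus fails four of the four routes that turn on relatedness and none of the four that do not.

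**The case against.** The strongest reply is that the sentence is permissive and sits inside a sensible definition. It says that such an event may be graded Unlikely. The governing idea is that the link is doubtful, and the sentence before it directs the assessor to exposure, not to minutes of administration. A study physician who thinks the drug more likely than not caused the event should grade it Probable. This stands in part: the clause compels no misgrading, and Probable and Unlikely do not truly overlap, because Probable also requires that judgement of cause. But the plan never says how long exposure lasts, and the clause then treats the end of administration as informative.

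Second, the reporting table requires events to be serious and unexpected as well as related. The common reactions listed under Allergic/anaphylactic reaction (diarrhea, constipation, hypertension) would usually miss the expedited route on those grounds whatever their grade. This stands, and they are not evidence of harm from the clause. What remains is the serious unexpected event.

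Third, several routes ignore attribution, including one-business-day reporting of infusion reactions to the DSMB. This also stands. Those routes lead to the PI, DSMB or DMC, however, and do not replace the IRB and FDA expedited reports.

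Fourth, attribution also covers study procedures. A subject can stop the MRI, and whether claustrophobia or discomfort then settles is informative. This stands and limits the fix to the infusion.

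**Conclusion.** The concern holds for the ferumoxytol infusion. The clause is met by any AE that outlasts 30 minutes of administration, including a reaction that led to the infusion being stopped, and it conflicts with the protocol's own description of continuing exposure. It permits, without requiring, a grade that fails all four relatedness-based routes. The practical reach is narrow: serious, unexpected events for which the assessor relies on this sentence.

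Two stronger readings are tempting and are not supported:

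- A reader might infer that an Unlikely event escapes all reporting. It does not: DSMB reporting, the one-business-day route, OnCore access with SAE notice, and the anaphylaxis stopping rule carry no relatedness condition.
- A reader might infer that related-event rates will be biased downward, by 5 percentage points per regraded event (1/20). The documents define no related-event rate as an endpoint, and nothing shows how often assessors would use the clause. The wording opens a possibility of under-grading and of inconsistency between assessors; a bias is not demonstrated.

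The conclusion rests on reading the clause literally and on the clearance times in Impact on the Fetus as stated. The delivery dates assumed above do not affect it.

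**What to change.** In Assessment of Attribution, under Unlikely Related:

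1. State that, for the ferumoxytol infusion, persistence of an AE after the infusion has ended or been stopped does not support a grade of Unlikely.
2. State that timing is judged against exposure that continues after administration, and reconcile this with both clearance statements in Impact on the Fetus and with the instruction in the Data and Safety Monitoring Plan on stopping the infusion. Do not set a 24-hour cut-off: the protocol gives two clearance times, and the shorter one could itself push later maternal or fetal events toward Unlikely.
3. If the dechallenge wording is wanted, keep it for the MRI procedures only.

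The cost is a few sentences and a short briefing for those who assign attribution. No new data and no change in clinical management are needed. The downside is that a few more events may be graded possibly related and reported.
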